## B. Study Endpoints

**1) Primary outcome:** The Aim 1A outcome is saliva cotinine-verified 7-day smoking abstinence at 12 weeks. Participants who report not smoking in the past 7 days and have a saliva cotinine level of <10 ng/mL at the week 12 timepoint will be considered abstinent.

**2) Secondary outcome:** The Aim 1B outcome is 7-day smoking abstinence at 24 weeks, based on self-report and verified by a salivary cotinine level of <10 ng/mL.

**3) Other outcomes:** Other outcomes include 7-day smoking abstinence at weeks 1-11 (defined as no smoking the past 7 days and having a point-of-care saliva cotinine level <30 ng/ml), use of varenicline or other smoking cessation medications (assessed by self-report and BHCHP chart review), use of other tobacco treatment resources, changes in past-month drug and alcohol use and psychiatric symptoms (assessed with the AUDIT, DAST-10, drug use inventory, PHQ-9, GAD-7, at 12 and 24 weeks).

### C. Statistical Methods

**Quantitative analysis:** Quantitative analysis will be based on the intention-to-treat principle. We will use Chi-squared tests to assess the difference between arms on attainment of the primary and secondary outcomes. Cochran-Mantel-Haenszel tests will determine whether the intervention effect is homogenous across study sites. We will use logistic regression to assess the intervention effect while adjusting for site. In primary analysis, participants who do not provide a saliva sample or are lost to follow-up will be assumed non-abstinent. A sensitivity analysis will use multiple imputation to impute missing outcomes data based on non-missing variables. In addition to cross-sectional analyses of the primary and secondary outcomes, we will conduct a repeated measures analysis of smoking status at 12 and 24 weeks to assess the overall impact of financial incentives on smoking abstinence. This analysis, which provides greater statistical power than cross-sectional analyses, will use generalized estimating equations (GEE) to account for the correlated data structure. We will also use GEE to analyze the other outcomes of changes in cigarette consumption, WHO ASSIST drug and alcohol scores, and mental health scores, each measured at baseline and 12 and 24 weeks.

**Qualitative analysis:** All interviews will be transcribed verbatim by a professional service and analyzed using NVivo 11 software. Data analysis will be based on a grounded theory approach and will occur concurrently with data collection to ascertain when thematic saturation is reached for each sampling stratum. Two trained study staff members, working in parallel under the direction of Drs. [name], [name], and [name], will begin by open-coding the raw transcript data to form initial categories using a principally inductive approach. During weekly team meetings, the method of constant comparison will be used to iteratively refine these categories, to resolve discrepancies through discussion and reference to raw data until high inter-rater reliability ( $K \geq 0.80$ ) is achieved, and to organize emergent major and minor themes into a hierarchical framework. Analyses will compare findings across treatment response profiles to generate insights about the reasons for response variability. Consistent with the embedded-experiment mixed methods design, the qualitative data will be used to answer the basic question: "To what extent do the qualitative process findings enhance the understanding of the experimental outcomes?" Toward that end, the qualitative findings will be included in the main paper reporting the RCT results to provide a more nuanced picture of why and how the intervention produced the outcomes it did. Subsequent papers will make further use of the qualitative data to examine why certain subgroups fare better with financial incentives, to introduce a conceptual framework for incentive-based health interventions for homeless

individuals, to share lessons learned about the practicalities of designing and deploying an incentives intervention for this population, and to inform future modifications of the intervention.

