## **IV. SUBJECT ENROLLMENT**

### **A. Methods of enrollment**

Participant screening, enrollment, and randomization will take place over the course of 3 visits:

- 1) Screening visit: Individuals recruited through the above methods will be screened for study eligibility. Prospective participants who approach study staff during prespecified open-screening sessions at clinic sites will complete the entire eligibility screen in-person. Prospective participants who call study staff directly or who are proactively contacted for recruitment over the phone will be given the option to complete the eligibility screener questions over the phone and then complete the saliva cotinine test in-person at JYP (see section V.A.). We anticipate screening up to 1000 people in order to reach our target of 180 randomized participants.
- 2) Enrollment visit: Individuals who are eligible for the study will be invited to attend a study enrollment visit for written informed consent, collection of demographic and contact information and assessment of baseline measures.
- 3) Randomization and baseline clinician visit: Individuals who complete the enrollment visit and baseline survey will be asked to return for a baseline clinical evaluation by the study clinician. The study clinician will evaluate participants to determine if a varenicline prescription is appropriate and will provide the initial prescription for varenicline in most cases (see section V.A. for details). Concurrently, participants will be randomized to the control arm (N=90) or financial incentives arm (N=90). Randomization will be stratified by housing status (currently homeless vs. currently housed). Following randomization, staff will set up a brief introductory video on a tablet to orient participants to their study arm. Participants without a mobile phone will be provided one with a prepaid voice and text plan to facilitate communication and follow-up (see section V.C. for details).

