### C. Treatment assignment

Participants will be randomized 1:1 to the control arm (n=90) or the financial incentives arm (n=90). Randomization will be stratified by housing status to ensure balanced representation of housed and homeless individuals across the 2 study arms. The attached Study Schema provides an integrated summary of the screening, enrollment, and randomization procedures along with the components of each study arm and the principal study outcomes.

The 2 study arms are as follows:

**1) Control arm (n=90):** Participants in this arm will be offered 12 weeks of varenicline and 5 sessions of tobacco coaching. As an attention control to help ensure a similar level of contact to the financial incentives arm, control arm participants will have the option to attend 10 cotinine monitoring visits over 12 weeks during which they would submit saliva samples for cotinine testing and receive a fixed debit card payment, irrespective of the result.

**2) Financial incentives arm (n=90):** Participants in this arm will be offered 12 weeks of varenicline and 5 sessions of tobacco coaching in a manner identical to the control arm. These participants will also have 10 cotinine monitoring visits over a 12-week period where they will receive debit card payments for saliva cotinine levels <30 ng/ml.

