#### H. Procedures for Restarting Enrolled Participants

As described in protocol amendment 11, all study activities were paused on 07/06/21 due to a global shortage of varenicline resulting from elevated levels of nitrosamine contaminants prompting a recall of all Pfizer-manufactured varenicline on the market. The safety considerations related to this are addressed in section VII.B. At the time of study suspension, 11 participants were enrolled.

Once the study resumes, the 11 participants who were previously enrolled will be approached by phone or in person to be invited to restart the study. Participants interested in restarting the study will do so under their original study ID number and randomized group assignment but will be asked to redo all other study activities. If participants are interested in restarting the study, they will be asked to complete the eligibility screener questions and saliva test (see section V.A.1.) to confirm their continued eligibility before completing two study restart appointments as described below.

To ease the response burden, participants will be offered the option to complete the eligibility screener questions over the phone. If their responses to the questions suggest that they are still eligible to participate, they will be invited to meet with study staff in person at JYP within two weeks to confirm their eligibility with a saliva test for cotinine. If the cotinine saliva test is consistent with current smoking, participants will immediately proceed with the first study restart appointment. Participants who opt to complete all components of the eligibility re-screening in person will meet with study staff at JYP and, if still eligible, will be invited to complete the first study restart appointment either immediately or within 2 weeks. Participants who are found to no

longer be eligible during any component of the eligibility re-screening process will be given the option to either screen again at a later date (if the reason for ineligibility is a time-limited issue such as connectedness to care) or to unenroll from the study.

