At the first study restart appointment, participants will follow procedures similar to the enrollment appointment discussed in section V.A.2. Study staff will review an updated version of the consent form with participants, and participants will be required to sign this updated version of the consent form to continue study participation. Study staff will then confirm participants' current demographic and contact information and repeat the full baseline survey. Participants will receive \$25 for completing this first appointment. Following this first appointment, all PCPs will be messaged using the same procedures described in sections V.A.4 and V.B. PCPs will need to give permission for the study clinician to prescribe varenicline for participants who report various health concerns during their most recently-completed eligibility screener and baseline survey.

The second study restart appointment must be completed within 4 weeks of the first study restart appointment. Participants will follow the same procedures described in sections V.A.3 and V.A.4, with the exception that participants who were previously randomized will retain their original treatment group assignment. Participants who do not have their own phone will be offered a study phone and will be paid \$10 for completing this study visit.

Participants who complete both the first and second appointments will restart the study at week 0, which corresponds with the quit date and first tobacco coaching session, approximately 1 week after their second study restart appointment.

All data collected during the original study launch prior to the pause will be exported from REDCap and archived in the secure Lab Archives system to allow for a clear audit trail of any changes to the data. In REDCap, new instances of forms will be created for any repeatable forms, and new data will overwrite old data as needed for non-repeatable forms. Study staff will log all instances of updates to existing non-repeatable forms within REDCap. The most recent data will be used for analyses and earlier data will be disregarded.

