#### D. Power Analysis

Our power calculation is based on the Aim 1A outcome of cotinine-verified smoking abstinence at 12 weeks. With a sample arm of 90 per arm, we will have >80% power to detect a difference in abstinence at 12 weeks of 4% in the control arm and 17.5% in the incentives arm at a two-tailed p of 0.05.

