The qualitative interviews conducted at 12 and 24 weeks will be recorded by a microphone connected directly to a password-protected, Mass General Brigham-approved laptop or tablet with full-disk encryption. Audio files will be backed up to the PI's SFA described above and then deleted from the portal device.

The study data will be examined on a weekly basis by the REDCap database programmer, working in conjunction with the PI, to identify patterns of missing data or non-response, to ensure that critical variables are being captured and recorded as intended, and to generate recruitment and enrollment reports for review by the PI in conjunction with the co-investigators. Free-text notes recorded by data collectors will be examined to identify potentially problematic items that may require additional clarification. The database programmer will prepare cleaned, de-identified analytic datafiles for use by the biostatistician to conduct the data analyses described in the Research Strategy. Analyses will occur periodically throughout the study and

the findings will be reported in annual progress reports to the NIH and in continuing review reports for the Mass General Brigham IRB.

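### Housing status is the only stratification factor at randomisation, but no named analysis uses it; a housing-stratified test would gain a little power if housing predicts abstinence.

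*Combined protocol and SAP*

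**What the plan says.** Section IV.A sets the stratification factor: "Randomization will be stratified by housing status (currently homeless vs. currently housed"). Section IV.C repeats it with its purpose: "Randomization will be stratified by housing status to ensure balanced representation of housed and homeless individuals across the 2 study arms". No other factor is named.

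Section VI.C gives the analysis of the 12-week primary and 24-week secondary outcomes: "We will use Chi-squared tests to assess the difference between arms on attainment of the primary and secondary outcomes". It adds CMH tests to examine homogeneity across sites, and then: "We will use logistic regression to assess the intervention effect while adjusting for site". Multiple imputation and GEE models follow without a covariate list, so housing is not ruled out there, but it is not named either.

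Section VI.D sizes the trial at 90 per arm for "a difference in abstinence at 12 weeks of 4% in the control arm and 17.5% in the incentives arm", with more than 80% power at a two-sided 0.05.

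Two other places bear on any change. Section V.H says of the 2021 pause: "At the time of study suspension, 11 participants were enrolled". Those who restart keep any assignment already made but repeat the baseline survey, and "The most recent data will be used for analyses and earlier data will be disregarded". Section IX.A says: "Analyses will occur periodically throughout the study".

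**The concern.** Stratifying makes the arms more alike on housing than chance alone would. If housing also predicts abstinence, the true variance of the difference between arms is smaller than the variance the ordinary chi-squared test assumes. The test then rejects slightly less often than 5% under the null and gives up a little power. A test stratified by the same factor uses the smaller variance.

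The plan instead adjusts for site, on which it did not stratify. Section III.B says recruitment starts at one venue and may extend to two more, so site may turn out to have a single level. Housing status is known for everyone randomised.

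Only efficiency is at stake. Neither the validity of the planned test nor the power claim is in question.

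**Working it through.** **The plan's own figure.** Inputs from VI.D: 90 per arm, 4% and 17.5%, two-sided 0.05. The pooled rate is (4 + 17.5)/2 = 10.75%.

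- Null SE = √(2 × 0.1075 × 0.8925 / 90) = 0.0462
- Alternative SE = √((0.04 × 0.96 + 0.175 × 0.825) / 90) = 0.0451
- Power = Φ((0.135 − 1.96 × 0.0462) / 0.0451) = 83.8%

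Exact enumeration of the uncorrected chi-squared test gives 86.9%. Both support the claim of more than 80%.

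**Assumptions.** The documents give no share currently homeless and no housing-abstinence association. I take the share as 50-70% and the odds ratio (OR, housed versus homeless) as 1 to 5, holding the overall rates at the plan's values.

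**Size of the chi-squared test, one case by hand.** Take 70% homeless, OR 5 and an overall null rate of 10.75%. The stratum rates are 5.6% and 22.8%.

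- Within-stratum variance = 0.7 × 0.056 × 0.944 + 0.3 × 0.228 × 0.772 = 0.0898
- Variance used by the chi-squared test = 0.1075 × 0.8925 = 0.0959
- Ratio = 0.936, so the effective critical value is 1.96/√0.936 = 2.026 and the size is about 0.043

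Simulation with arms balanced within strata gives 0.0435 for chi-squared and 0.0484 for the housing-stratified CMH test.

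**Power.** With *n* per arm in a stratum, *y* abstainers in the incentives arm, *t* abstainers in both arms and N = 2*n*, the CMH statistic is [Σ(y − t/2)]² / Σ[n² t(N − t) / (N²(N − 1))]. It is compared with 3.84, without continuity correction. Results from 400,000 simulated trials per setting, arms balanced within strata, 4% versus 17.5%:

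| Homeless share | OR | Chi-squared | CMH by housing | Gain (points) |
|---|---|---|---|---|
| 50% | 1 | 0.8687 | 0.8689 | 0.0 |
| 50% | 2 | 0.8708 | 0.8716 | 0.1 |
| 50% | 3 | 0.8724 | 0.8744 | 0.2 |
| 50% | 5 | 0.8752 | 0.8803 | 0.5 |
| 70% | 1 | 0.8692 | 0.8694 | 0.0 |
| 70% | 2 | 0.8709 | 0.8719 | 0.1 |
| 70% | 3 | 0.8725 | 0.8752 | 0.3 |
| 70% | 5 | 0.8775 | 0.8848 | 0.7 |

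**Sensitivity.**

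- Permuted blocks of 4 within strata (block size assumed): gain 0.17-0.20 points at OR 2, 0.40-0.50 at OR 3, 0.79-1.14 at OR 5.
- More extreme inputs, balanced: with 20% housed the gain is 0.9 points at OR 5; at OR 8 it is 0.9-1.8 points for 20-50% housed.
- Not blocked within strata, OR 1: a loss of 0.19-0.26 points.

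**Sparse events.** Expected abstainers are 90 × 0.04 = 3.6 and 90 × 0.175 = 15.75, in total 19.35. A logistic model with arm and housing has 19.35/2 = 9.7 events per term. Adding a three-level site makes four terms, 19.35/4 = 4.8 per term. The chance of no control-arm abstainer, which leaves the logistic arm coefficient inestimable, is 0.96^90 = 2.5%. The chance that at least one housing stratum has no control-arm abstainer is 29% to 55% over OR 1 to 5, but the pooled CMH statistic is still defined.

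**Restarted participants.** At most 11/180 = 6.1% are affected.

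**The case against.** The strongest reply is that this is a preference. An unadjusted chi-squared test, named in advance, is valid and contradicts nothing in the plan. Section IV.C gives balance as the purpose of stratifying, and the design can deliver that without an adjusted test. The gain is a fraction of a point on power of about 87%. It also rests on an association the documents do not give: section III.A reports similar smoking rates in currently and formerly homeless people, which offers no hint of a large housing effect, although it does not concern success in quitting. All of this stands, and it is why the point is minor.

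A second reply is that the sign of the effect depends on how the allocation list was built. With 90 per arm fixed and housing left unbalanced, the CMH test loses 0.38-0.45 points at OR 1 and still loses 0.16-0.19 at OR 2. But that is not the stratified randomisation that IV.C describes. What remains is that the documents do not state the blocking, so a gain at modest odds ratios needs near-balance within strata.

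A third reply is that changing a primary test mid-trial costs credibility, and that nobody outside can see whether outcomes have already been compared by arm. Section IX.E rules out a formal interim analysis, but IX.A has analyses under way during the study. This limits when the change can be made. It does not remove the case for making it.

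**Conclusion.** The point holds as a minor one. Housing is the only stratification factor, and no analysis in VI.C names it. With a homeless share of 50-70% and arms balanced within strata, a housing-stratified CMH test gains about 0.1 points of power at OR 2, 0.2-0.3 at OR 3 and 0.5-0.7 at OR 5, while the size of the chi-squared test falls to about 0.044 at OR 5. If housing is not prognostic the gain is zero, or a loss of 0.2-0.3 points where allocation is not blocked within strata. Over these shares and OR 1 to 5, power lies between 0.86 and 0.885 with either test. The planned test stays valid and the sample size needs no change. The textual finding is certain; the size of the benefit depends on the assumed share and odds ratio.

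**What to change.** Amend section VI.C, with a date, before any comparison of outcomes by arm:

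- Make the 12- and 24-week test a CMH test stratified by housing status as used at randomisation. Living situation is asked again at weeks 12 and 24 (VI.A), so the wording should fix the randomisation value.
- Include housing status in the logistic and GEE models. With about 19 abstainers expected, let the CMH test carry the primary inference and treat the adjusted logistic model as supportive.
- State that restarted participants who had already been randomised are analysed in the stratum used for their original assignment, as an exception to the most-recent-data rule in V.H.
- Confirm in the same text whether allocation was blocked within housing strata.

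If outcomes have already been compared by arm, keep the chi-squared test as primary and report the housing-stratified test as supportive.

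The cost is a short amendment. No new data are needed: housing status is required to randomise, and V.H says the pre-pause data are archived. The statistical downside is the 0.2-0.3 point loss described above, and only if housing is not prognostic and allocation is unblocked within strata.

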## II. SPECIFIC AIMS

To address the above gaps in evidence, we will conduct a community-based RCT of financial incentives for smoking abstinence among adult smokers at BHCHP. Recognized as a leader in homeless health care, BHCHP serves 12,000 currently and formerly homeless patients annually throughout greater Boston. We will randomize 180 participants recruited from 3 BHCHP sites: a shelter clinic, a day center clinic, and a medical center clinic. All participants will be offered 12 weeks of varenicline, 5 sessions of tobacco coaching, and 10 cotinine monitoring visits over a 12-week period. Participants randomized to the financial incentives arm (n=90) will receive escalating debit card payments (range \$25-\$70) at each monitoring visit for saliva cotinine levels <30 ng/ml. Control arm participants (n=90) will receive a fixed payment (\$10) at each monitoring visit regardless of their saliva cotinine level. We will use an embedded-experiment mixed methods design, where qualitative ('qual') data collection is embedded within a larger quantitative ('QUAN') RCT with the following specific aims:

**Aim 1. (QUAN)** To determine the effect of the financial incentives intervention on cotinine-verified 7-day smoking abstinence at **A**) the end of treatment (12 weeks) and **B**) 12 weeks after treatment (24 weeks).

*Hypotheses:* Incentive arm participants will have significantly greater cotinine-verified 7-day smoking abstinence than control arm participants at **A**) 12 weeks and **B**) 24 weeks.

**Aim 2. (qual)** To assess why, how, and under what circumstances homeless smokers **A**) achieve abstinence in response to financial incentives and **B**) maintain abstinence after incentives are stopped.

Interviews with participants at **A**) 12 weeks (N=30) and **B**) 24 weeks (N=20) will examine cognitive ('why?'), procedural ('how?'), and contextual ('under what circumstances?') dimensions of their response to financial incentives to generate hypotheses about potential mechanisms for on-treatment and post-treatment effects and to inform modifications of the intervention for future use.

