We will not exclude individuals who use alcohol or other drugs, as long as they meet all of the above eligibility criteria. This decision was made because our prior survey of homeless smokers in Boston suggested that limiting the trial to individuals who do not use other drugs or alcohol would considerably narrow the pool of potentially eligible participants and would severely limit the generalizability of our findings. Concomitant drug and/or alcohol use is common among homeless smokers, and smoking interventions for this population must contend with that reality in order to be applicable. In our pilot RCT, we found that drug and alcohol use, assessed serially over 8 weeks, did not change among participants assigned to receive financial incentives for smoking abstinence. Furthermore, evidence suggests varenicline is both safe and effective in patients with a history of substance use disorder. Because of the potential importance of this issue, we again plan to assess drug and alcohol use with a validated instrument at the beginning, middle, and end of the trial, and to conduct interaction analyses to determine whether drug and alcohol use severity modify the effect of the intervention.

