#### B. Source of subjects and recruitment methods

This study will be registered with ClinicalTrials.gov prior to the recruitment and enrollment of human subjects. All participants will be recruited from BHCHP clinical sites. BHCHP does not have its own IRB but instead will rely on the Mass General Brigham Human Research Committee for IRB review through a reliance agreement initiated through SMART IRB. In addition to being a faculty physician-investigator at Massachusetts General Hospital and Harvard Medical School, the study PI has over 20 years of clinical experience with homeless patients and more than 13 years of research experience relating to the health of homeless people. He has been a staff physician at BHCHP since 2008 and was named the Director of Research at BHCHP in 2017.

Recruitment of study participants will occur at up to 3 venues; however, initial efforts will focus on the first of these sites:

*a) Medical center venue:* Jean Yawkey Place, adjacent to Boston Medical Center, is the BHCHP headquarters facility where medical, behavioral health, and dental clinics operate 5 days per week with an on-site pharmacy and medical respite unit. Compared to other BHCHP locations, Jean Yawkey Place has the highest volume of patients, the most space, and the greatest flexibility in space configuration. This will allow study personnel to conduct in-person participant recruitment while practicing COVID-appropriate social distancing and prioritizing the health and well-being of both participants and study staff.

Depending on the status of the COVID-19 pandemic, recruitment may later expand to two additional locations when safe to do so:

- b) Shelter venue:* Pine Street Inn is a 470-bed shelter serving both men and women where BHCHP operates a medical clinic 7 days per week in the men's shelter and 6 days per week in the women's shelter.
- c) Day center venue:* St. Francis House is a multiservice day center for homeless people where BHCHP operates a medical clinic 5 days per week.

Study participants will be recruited through five methods:

- a) Self-referral:* Study staff will be stationed in heavily trafficked areas within the recruitment sites at prespecified times each week. We anticipate that a general awareness of the study due to study staff presence and word-of-mouth will encourage prospective participants to approach study staff and undergo eligibility screening if interested.

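### The plan uses the Cochran-Mantel-Haenszel test to judge whether the effect is the same at every site, a question that test does not address

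*Combined protocol and SAP*

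**What the plan says.** Section VI.C (Statistical Methods) lists three analyses involving arm or site for the binary abstinence outcomes:

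- The comparison of arms: "We will use Chi-squared tests to assess the difference between arms on attainment of the primary and secondary outcomes".
- The site check: "Cochran-Mantel-Haenszel tests will determine whether the intervention effect is homogenous across study sites".
- The adjusted estimate: "We will use logistic regression to assess the intervention effect while adjusting for site".

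No arm-by-site term and no test of equal odds ratios is named there or elsewhere. The only interaction analyses in the document are in section III.A, where the investigators plan to "conduct interaction analyses to determine whether drug and alcohol use severity modify the effect of the intervention"; these do not involve site.

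The number of sites is described in two ways. Section II says "We will randomize 180 participants recruited from 3 BHCHP sites: a shelter clinic, a day center clinic, and a medical center clinic". Section III.B says "Recruitment of study participants will occur at up to 3 venues; however, initial efforts will focus on the first of these sites", with expansion to the other two depending on the pandemic. Randomization is stratified by housing status, not by site (sections IV.A and IV.C).

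**The concern.** The CMH null hypothesis is that arm and outcome are independent within every site, that is, a common odds ratio of 1. The statistic adds up observed minus expected counts over sites before squaring, so it measures the average site-adjusted effect.

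Neither possible result answers the question the plan sets. A significant CMH says there is an effect on average, whether or not it is the same everywhere. A non-significant CMH may mean no effect at any site, or effects in opposite directions that cancel.

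The venues differ in kind (a medical center, a shelter and a day center), so consistency across them is a reasonable thing to report. If more than one enrols and the sentence is followed as written, any statement in the report that the effect was or was not homogeneous would have no support.

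**Working it through.** **Inputs from the documents.** 90 per arm and 1:1 allocation (section IV.C); "4% in the control arm and 17.5% in the incentives arm" at a two-sided 0.05 (section VI.D); missing outcomes counted as non-abstinent, so all 90 per arm are analysed (section VI.C).

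**Assumed.** The split of participants by site and the site-specific rates, because the documents give neither.

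**1. The plan's own figure.** Power for 4% vs 17.5% with 90 per arm is stated as above 80%. The mean rate is 0.1075.

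- Null standard error: √(2 × 0.1075 × 0.8925 / 90) = 0.0462.
- Alternative standard error: √((0.04 × 0.96 + 0.175 × 0.825) / 90) = 0.0451.
- z = (0.135 − 1.96 × 0.0462) / 0.0451 ≈ 0.99, so power is 83.8%.

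Exact enumeration of the uncorrected Pearson test gives 86.9%. The stated figure is reproduced, and nothing below changes it.

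**2. Two constructed examples, 30 per arm per site, incentives vs control.**

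*(a) Identical effect at three sites, 6/30 vs 2/30 (odds ratio 3.5 at each).* At each site the expected count is 4 and the variance is 30 × 30 × 8 × 52 / (60² × 59) = 1.763. CMH = (3 × 2)² / (3 × 1.763) = 6.81, p = 0.009. Breslow-Day = 0, p = 1.0.

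*(b) Opposite effects: 12/30 vs 4/30, 4/30 vs 12/30, 8/30 vs 8/30 (odds ratios 4.33, 0.23, 1.0).* The deviations are +4, −4 and 0, so CMH = 0, p = 1.0. For Breslow-Day the pooled odds ratio is 1, the expected count at each of the first two sites is 8, and the variance is 1 / (1/8 + 1/8 + 1/22 + 1/22) = 2.933. The statistic is 2 × 4² / 2.933 = 10.9 on 2 df, p = 0.004.

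Read as a homogeneity test, CMH gives the wrong answer in both: it is significant when the sites agree exactly and null when they conflict.

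**3. Simulated rejection rates at two-sided 0.05.** CMH is without continuity correction. There were 200,000 runs for CMH and Breslow-Day-Tarone (BDT), and several thousand for Zelen's exact test.

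| Assumed pattern | CMH | BDT | Zelen |
|---|---|---|---|
| Same effect (4% vs 17.5%), three sites of 30 per arm | 87% | 4% | 3% |
| Control 4%; incentives 25%, 17.5%, 10%; three sites of 30 per arm | 87% | 10% | 8% |
| Two sites of 45 per arm: 4% vs 31%, and 4% vs 4% | 88% | 49% | about 32% |
| Two sites of 45 per arm: 4% vs 17.5%, and 17.5% vs 4% | about 5% | 87% | 77% |

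The first three rows keep the overall rates at the planning values: (25 + 17.5 + 10) / 3 = 17.5, and (31 + 4) / 2 = 17.5. The last row does not. It is an extreme bound with (4 + 17.5) / 2 = 10.75% in both arms, hence no overall effect.

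For the same-effect case CMH stays at 87% with splits of 60/15/15, 70/10/10 or 45/45 per arm. With a continuity correction, the first three CMH values become 79%, 80% and 82%, the same pattern.

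**4. How much a correct test could show.** Expected events are 90 × 0.04 + 90 × 0.175 = 19.4. At 4%, the chance that at least one of three control groups of 30 has no events is 1 − (1 − 0.96³⁰)³ = 0.65. An ordinary arm-by-site logistic term would therefore often have no finite estimate.

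**The case against.** The strongest reply concerns weight. Homogeneity across sites is not an aim, hypothesis or endpoint, and the plan ties no decision to it: there is no pooling rule and no change of model. Recruitment may stay at one venue, in which case the question disappears. A correct test would also be weak, at 8–10% power for the moderate pattern and about a third for Zelen even when the whole effect sits at one of two sites. On this view the sentence is a mislabelled ancillary test.

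All of this is true, and it limits the consequence. It does not rescue the sentence, which gives CMH a task it cannot perform. Low power for a correct test is a reason to report site-specific estimates and avoid a claim of homogeneity; it gives no support to a test of a different hypothesis.

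A second reply is that some software prints a homogeneity test beside CMH, and that may be what was meant. The plan names no such test, so the text does not support that reading.

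A third is that the choice of replacement is partly preference. A likelihood-ratio or penalised arm-by-site test can be computed despite zero cells, and sparse cells also strain the Breslow-Day approximation. That stands: any valid homogeneity test would cure the error. Zelen's test is suggested first because it is exact with few events.

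**Conclusion.** The concern holds. The method is wrong for its stated purpose, and nothing else in the plan supplies the missing test. At the planning rates CMH is significant in 87–88% of trials whether the effect is identical across sites, moderately different, or confined to one of two sites, so its result cannot support a statement in either direction.

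These percentages rest on assumed site sizes and site rates. The conclusion itself does not, because it follows from the hypothesis that CMH tests. The impact is limited to a secondary consistency check and arises only if more than one venue enrols. The point should be fixed, but it does not threaten the main result.

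**What to change.** Replace the CMH sentence in section VI.C with wording such as: *If more than one site enrols, homogeneity of the odds ratio across sites will be assessed by Zelen's exact test (or Breslow-Day with Tarone's correction) as an exploratory analysis, with site-specific estimates and confidence intervals; the Cochran-Mantel-Haenszel test will be used for the site-stratified test of the intervention effect.*

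Add one sentence stating that, with about 19 expected events, the homogeneity test has low power for moderate differences, so a non-significant result does not show homogeneity. The illustrative figure is about 8–10% for incentive-arm rates of 25%, 17.5% and 10% against 4% control, assuming 30 per arm per site.

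The cost is one sentence replaced and one added. No new data are needed, and the primary analysis and sample size do not change.
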